2.2.1 Rationale for Biomarker Assessment

The primary goal of the biomarker assessments for this study is to evaluate potential mechanisms of resistance to asciminib.

Exploratory endpoints involving biomarker assessments for patients treated with asciminib, in comparison to those treated with bosutinib, will focus on 1) the PK/PD relationship; 2) BCR-ABL1 gene mutations that could influence the outcome of treatment regimens; and 3) the underlying biology of CML.

In order to evaluate tumor kinetics on a molecular level and to explore the role of mutations with respect to response to treatment, exploratory endpoints include assessment of mutations in the BCR-ABL1 gene at Week 1 Day 1, upon confirmed loss of molecular response and/or at end of treatment. Mutational status will be characterized in peripheral blood.

2.3 Rationale for dose and regimen selection

The dose and regimen of asciminib selected for this study is 40 mg BID. This dose is supported by pharmacokinetic, efficacy and safety data available from the ongoing [CABL001X2101] study.

During escalating doses of asciminib 10 mg to 200 mg on a continuous BID schedule in study [CABL001X2101], the 40 mg BID dose was shown to be active and well tolerated in CML-CP patients.

With respect to efficacy, no clear evidence of dose-response relationship was observed across dose levels when considering Complete Cytogenetic Response (CCyR) or MMR. However, as described below, PK-PD population modeling using change from baseline of BCR-ABL1 mRNA levels as a PD endpoint suggest a higher probability of achieving ≥ 1 log reduction at 6 and 12 months with 40 mg BID versus 20 mg BID.

With respect to safety, although no MTD (maximum tolerated dose) has been formally characterized, there is an increased toxicity observed at doses ≥ 80 mg BID (pancreatitis occurred at the dose of 80 mg in two patients who had an intra-patient escalation to 80 mg from 40 mg, and in one patient at the dose of 150 mg BID). Generally there is a trend for higher rates of discontinuation due to AE, DLT (dose limiting toxicity) and grade 3/4 AE with increasing doses.

With respect to overall exposure, the dose of 40 mg BID is expected to result in concentrations consistently above IC₉₀ *in vitro* concentrations. The estimates from study [CABL001X2101] were found to be above the threshold trough concentration required for 90% inhibition of pSTAT5 derived from a preclinical PK-PD KCL-22 mouse xenograft model (free IC₉₀: 30 to 121 ng/mL, after correction for protein binding) and *in vitro* gIC₅₀ assessed in the KCL-22 cell line (1 ng/mL = 2.1 nM after correction for protein binding).

A preliminary population PK-PD model has been developed using data from the [CABL001X2101] study (cut-off 2 May 2016). The time course of molecular response (change in BCR-ABL1 ratio % IS levels from baseline) was described using a semi-physiological model accounting for cell maturation, disease progression and existing resistance. Simulations performed (with 100 patients) using asciminib population PK-PD model revealed that at a dose of 40 mg BID, ~41% (CI₉₅%; 31-51%) of chronic phase CML patients having failed ≥ 2 TKI or intolerant to TKIs are likely to exhibit a 1 log₁₀ reduction of (%) BCR-ABL1 mRNA transcript levels from baseline at 6 months, and 53% (CI₉₅%; 43-63%) at 12 months, and predicting higher probability of achieving BCR-ABL1 mRNA ≥ 1 log reduction at 6 and 12 months with 40 mg BID versus 20 mg BID.

Additional preliminary PK-efficacy and PK-safety analyses to assess the exposure-response relationship for asciminib were conducted ([Section 1.2.1.2](#)). The efficacy measure used was Molecular Response (MR) which is defined as a decline in BCR-ABL1 transcript levels in clinical blood samples of patients with Chronic Myeloid Leukemia (CML). MR was evaluated as both a continuous variable (BCR-ABL1 transcript levels) and categorical variable (whether or not adequate decline in BCR-ABL1 was achieved). The safety measures used were occurrence of Common Toxicity Criteria (CTC) grade 2, 3 or 4 laboratory values for lipase and amylase.

Reviewing the totality of the efficacy, safety, and pharmacokinetic data derived from the [\[CABL001X2101\]](#) study, the recommended dose for asciminib in this phase 3 study is 40 mg BID. Of note, the dose of asciminib single agent BID is further being evaluated in patients with the T315I mutation. At present the recommended dose of 40 mg BID is for patients without the T315I mutation. For this reason, patients with the T315I mutation are excluded from this study.

2.4 Rationale for choice of combination drugs

Not Applicable.

2.5 Rationale for choice of comparators drug bosutinib

The guidance provided by the NCCN and the ELN ([Baccarani et al 2013](#)), recommends bosutinib as a treatment in CML-CP patients who fail first-line or second-line treatment with imatinib or nilotinib or dasatinib. Consistent with these recommendations and clinical practice, bosutinib was selected to be an appropriate comparator in a study of 3rd line CML-CP patients after failure of at least 2 prior TKIs, and is the comparator that will be used in the present study.

It is to be noted that bosutinib has no activity against the T315I and V299L mutant form of BCR-ABL1. Patients who have the T315I or V299L mutations documented in their medical record will already be excluded from this study. Bosutinib is known to be active against E255K/V, F317L/V/I/C, F359V/C/I, T315A, and Y253H and therefore, these mutations are not considered in the exclusion criteria for the current study.

Ponatinib is not selected as the comparator in the present clinical trial, because the comparator in this study needs to be an approved agent administered at the approved dose. Currently, the ponatinib dose is being evaluated in a randomized trial as a post-approval commitment due to the occurrence of vascular risks at the current approved dose of ponatinib. The dose of ponatinib that will be approved and will be used in practice at the completion of the present study may not be the approved dose at the time of initiation of the present study.

2.6 Risks and benefits

Appropriate eligibility criteria, as well as specific dose modification and stopping rules in the event of expected toxicities, are included in this protocol. Recommended guidelines for prophylactic or supportive treatment for expected toxicities, including management of study-drug induced adverse events are provided in [Section 6.3](#). Patients who have failed 2 prior TKIs are at increased risk of progression to more advanced phases of CML such as CML-AP and CML-BC. Currently available therapeutic agents in this setting are non-curative and patients remain at risk of progressing after short duration of remissions ([Khoury 2012](#)).

An important potential risk for patients enrolling on the experimental arm of the study with asciminib will be that this agent may be ineffective. However, the evidence to date at the doses to be administered in a similar population of patients in the study [CABL001X2101] suggests that asciminib is an active agent. Further, the adverse event profile of asciminib is similar qualitatively to that observed with other TKIs targeting BCR-ABL1 (Section 1.2.1.2). The risk of asciminib not being effective has been mitigated in that patients will be observed closely for evidence of efficacy, based on assessment of hematologic, cytogenetic and molecular response data, which will permit rapid decision making as to discontinuation of therapy if necessary.

Other risks to subjects in this trial will be minimized by compliance with the eligibility criteria and study procedures, close clinical monitoring, and adherence to dose modification and interruption guidance provided in the protocol.

The currently available information suggests that there is equivalence between the two arms with respect to benefit / risk to enable inclusion of patients in this study.

There may be unforeseen risks with asciminib which could be serious. Refer to the latest [Asciminib Investigator's Brochure] for additional details.

3 Objectives and endpoints

Objectives and related endpoints are described in Table 3-1 below.

[figure not shown]

Table 3-1 Objectives and related endpoints

[figure not shown]
Objective	Endpoint	Analysis
Primary		
To compare the MMR rate at 24 weeks of asciminib versus bosutinib	Major Molecular Response (MMR) rate at 24 weeks	Refer to Section 10.4
Key secondary		
To compare additional parameters of the efficacy of asciminib versus bosutinib	MMR rate at 96 weeks	Refer to Section 10.5.1
Other secondary		
To compare additional parameters of the efficacy of asciminib versus bosutinib	
 ● Cytogenetic response rate (Complete, Partial, Major, Minor, Minimal, no response) at and by all scheduled data collection time points including 24, 48 and 96 weeks ● MMR rate at all scheduled data collection time points (except 24 and 96 weeks which are already covered by primary and key secondary endpoints) ● MMR rate by all scheduled data collection time points including 24, 48 and 96 weeks ● Time to MMR ● Duration of MMR ● Time to CCyR ● Duration of CCyR ● Time to treatment failure ● Progression free survival ● Overall survival 	Refer to Section 10.5.2
To compare the safety and tolerability profile of asciminib versus bosutinib	Type, frequency and severity of adverse events, changes in laboratory values that fall outside the pre-determined ranges and clinically notable ECG and other safety data (vital signs, physical examination)	
To characterize the PK of asciminib in the CML-CP population	Trough plasma concentrations, PK parameters in full PK group: C _{max} , T _{max} , AUC _{0-12h} , CL/F	
To assess the safety of asciminib when administered as treatment after bosutinib failure according to the 2013 ELN Guidelines	Type, frequency and severity of adverse events, changes in laboratory values that fall outside the pre-determined ranges and clinically notable ECG and other safety data (vital signs, physical examination)	Refer to Section 10.6

Objective	Endpoint	Analysis
Exploratory		
To evaluate the influence of factors such as cytogenetic response at baseline, failure/intolerance to prior TKIs, line of therapy, gender, race and age on the effect of asciminib with respect to the primary efficacy endpoint	Major Molecular Response (MMR) rate at 24 weeks	Refer to Section 10.6
To explore the exposure-response relationships of asciminib; evaluate the effect of population covariates	Exposure-safety and exposure-PD analyses	
To characterize mutations in the BCR-ABL1 gene at Week 1 Day 1, upon confirmed loss of molecular response and/or at end of treatment and examine their association with molecular and cytogenetic response for asciminib vs. bosutinib	BCR-ABL1 gene mutations at Week 1 Day 1, upon confirmed loss of molecular response and/or at end of treatment as determined by Sanger Sequencing	
[REDACTED]	[REDACTED]	
To assess clonal evolution during treatment with asciminib vs. bosutinib	Low level BCR-ABL1 mutation profiles assessed by mass spectrometry at Week 1 Day 1, upon confirmed loss of MMR and/or at EOT. Clonal evolution of several genes implicated in CML assessed by Next Generation Sequencing (NGS) methods	
[REDACTED]	[REDACTED]	
To compare the impact of treatment on patient reported outcomes (PRO) including CML-specific symptoms, patient quality of life, and impact on work productivity and activity impairment from baseline and EOT between treatment arms in all patients	Change in symptom burden and interference from baseline over time according to the MDASI-CML PRO instrument Change in patient's impression of CML symptoms according to Patient Global Impression of Change (PGIC) Change in health utility from baseline over time according to EQ-5D-5L Change in work productivity and activity impairment over time according to WPAI	
To compare the impact of treatment on health care resource utilization between treatment arms in all patients	Health care resource burden over time	
To assess the efficacy of asciminib when administered as treatment after bosutinib failure according to the 2013 ELN Guidelines	
 • Cytogenetic response rate (Complete, Partial, Major, Minor, Minimal, no response) at and by all scheduled data collection time points • MMR rate at and by all scheduled data collection time points 	Refer to Section 10.6

Objective	Endpoint	Analysis
	
• Time to MMR• Duration of MMR• Time to CCyR• Duration of CCyR• Time to treatment failure	

4 Study design

4.1 Description of study design

The study is a phase 3, multi-center, open-label randomized study of oral asciminib versus bosutinib in patients with Chronic Myelogenous Leukemia in chronic phase (CML-CP), previously treated with 2 or more tyrosine kinase inhibitors.

The trial is designed to compare the efficacy and safety of asciminib with that of bosutinib in the treatment of patients with CML-CP having previously been treated with a minimum of two prior ATP-binding site TKIs. Patients intolerant to the most recent TKI therapy must have BCR-ABL1 ratio $> 0.1\%$ IS at screening and patients failing their most recent TKI therapy must meet the definition of treatment failure as per the 2013 ELN guidelines ([Baccarani et al 2013](#)). No more than 66 patients (approximately 30% of the overall trial population) that are intolerant to their most recent TKI therapy with BCR-ABL1 $< 1\%$ will be recruited in order to ensure that the CML third line patient population is adequately represented.

The study will also investigate secondary endpoints for efficacy, safety and PK of single-agent asciminib compared to bosutinib. Tolerability, PK, PRO and exploratory biomarker activities will also be assessed. Safety and efficacy data for patients switching to asciminib will be collected and analyzed separately.

Patients meeting all of the inclusion and none of the exclusion criteria will be randomized into one of the 2 treatment arms, based on a 2:1 randomization between the asciminib arm and the bosutinib arm.

[figure not shown]
The randomization will be stratified to ensure the study population is balanced between the arms with respect to cytogenetic response status (See [Section 7.2.1.2](#)) at screening as follows:

- Major cytogenetic response (complete or partial)
- No major cytogenetic response (minor, minimal or none)

Patients will continue to receive the assigned study treatments (asciminib or bosutinib) until the end of study treatment period as defined in [Section 4.3](#). Patients who discontinue their study treatment at any time during the study will be followed up for survival and for progression to AP/BC for up to 5 years from the date the last randomized patient receives the first dose (irrespective of treatment switch for patients failing bosutinib).

Serial PK samples over 12 hours will be collected on Week 2 Day 1 from at least 20 CML-CP patients (full PK group) on the asciminib arm, in addition to trough PK samples. These patients will be identified sequentially at selected sites that are capable of serial PK sampling over 12 hours. In the remaining patients in the asciminib arm and in patients that have switched to asciminib, sparse post-dose PK samples on Week 1 Day 1 and trough PK samples will be collected (sparse PK group).

Figure 4-1 Schematic of Study Design

4.1.1 Study treatment switch from bosutinib to asciminib

Patients with documented treatment failure (as per the 2013 ELN guidelines; [Baccarani et al 2013](#)) while on bosutinib treatment will have the option to switch to asciminib treatment within 96 weeks after the last patient has been randomized on study. The patients who switch to asciminib will be able to receive asciminib up to end of study treatment period. At the end of the treatment period for patients who, in the opinion of the investigator still derive clinical benefit, asciminib treatment will be made available through alternative options including, but not limited to, an expanded access/compassionate use/managed access program or access to commercial supplies in applicable countries. Discontinuation of asciminib for patients who have switched over from bosutinib must follow the guidelines provided in [Section 7.1.6](#). Eligibility criteria for patients switching to asciminib are described in [Section 7.1](#).

4.2 Timing of interim analyses and design adaptations

Not applicable. There are no formal interim analyses or design adaptations planned for this study. See [Section 8.6](#) for documentation of safety DMC.

4.3 Definition of end of study

The patients are treated in the study up to end of study treatment period defined as up to 96 weeks after the last patient receives the first dose or up to 48 weeks after the last patient has switched to asciminib treatment whichever is longer unless patients have discontinued treatment earlier. The end of the study, concluding the survival follow-up, will occur 5 years from the date when the last patient enrolled into the study receives the first dose of the randomized treatment.

The primary analysis (cut-off date) is defined as the date when all randomized patients have been on study treatment for 24 weeks ([Section 10.4](#)) or discontinued earlier. Subsequent to this

analysis, the primary clinical study report (CSR) will be developed. Following the cut-off date for the primary CSR, the study will remain open. Patients who are ongoing at the time of the primary analysis will continue to receive the assigned study treatments (asciminib or bosutinib) during the study treatment period as defined above. The end of study treatment analysis will be conducted with a cut-off date 30 days after the end of study treatment period to ensure all available treatment data from all patients in the study is analyzed and summarized in a CSR.

After the end of the study treatment period the assigned study treatment will be made available to patients who in the opinion of the Investigators are still deriving clinical benefit. This may be outside of this study through alternative options including, but not limited to, an expanded access/compassionate use /managed access program or access to commercial supplies in applicable countries.

Patients will be followed for survival and progression for up to 5 years from the date the last randomized patient receives the first study dose (irrespective of treatment switch for patients failing bosutinib). Information on subsequent treatments will also be collected. An updated analysis of OS and PFS will be performed at the end of the follow-up period in the final study CSR.

4.4 Early study termination

The study can be terminated at any time for any reason by Novartis. Should this be necessary, the patient should be contacted as soon as possible and instructed to stop taking study medication. The end of treatment visit should be scheduled and the same assessments should be performed as described in [Section 7](#) for a discontinued or withdrawn patient. The investigator may be informed of additional procedures to be followed in order to ensure that adequate consideration is given to the protection of the patient's interests. The investigator will be responsible for informing IRBs and/or ECs of the early termination of the trial.

5 Population

5.1 Patient population

Two-hundred and twenty-two (222) patients with CML-CP who had prior treatment with two or more ATP binding site TKIs will be randomized in a 2:1 fashion to receive either asciminib or bosutinib. No patients with a medical history of the T315I or V299L mutation at study entry will be included in the trial. Previous medical records should be used to confirm the patient's mutational status/history.

The definition of CML-CP will be according to the European Leukemia Network (ELN) criteria ([Baccarani et al 2013](#)), and is outlined below in the inclusion criteria.

The investigator or designee must ensure that only patients who meet all the following inclusion and none of the exclusion criteria are offered treatment in the study.

5.2 Inclusion criteria

Patients eligible for inclusion in this study have to meet **all** of the following criteria:

1. Male or female patients with a diagnosis of CML-CP \geq 18 years of age

2. Patients must meet all of the following laboratory values at the screening visit:
 - < 15% blasts in peripheral blood and bone marrow
 - < 30% blasts plus promyelocytes in peripheral blood and bone marrow
 - < 20% basophils in the peripheral blood
 - $\geq 50 \times 10^9/L$ ($\geq 50,000/mm^3$) platelets
 - Transient prior therapy related thrombocytopenia ($< 50,000/mm^3$ for ≤ 30 days prior to screening) is acceptable
 - No evidence of extramedullary leukemic involvement, with the exception of hepatosplenomegaly
- 3a. BCR-ABL1 ratio $> 0.1\%$ IS according to central laboratory at the screening examination, for patients intolerant to the most recent TKI therapy
4. Prior treatment with a minimum of 2 prior ATP-binding site TKIs (i.e. imatinib, nilotinib, dasatinib, radotinib or ponatinib)
5. Failure (adapted from the 2013 ELN Guidelines; [Baccarani et al 2013](#)) or intolerance to the most recent TKI therapy at the time of screening
 - Failure is defined for CML-CP patients (CP at the time of initiation of last therapy) as follows. Patients must meet at least 1 of the following criteria.
 - Three months after the initiation of therapy: No CHR or $> 95\%$ Ph+ metaphases
 - Six months after the initiation of therapy: BCR-ABL1 ratio $> 10\%$ IS and/or $> 65\%$ Ph+ metaphases
 - Twelve months after initiation of therapy: BCR-ABL1 ratio $> 10\%$ IS and/or $> 35\%$ Ph+ metaphases
 - At any time after the initiation of therapy, loss of CHR, CCyR or PCyR
 - At any time after the initiation of therapy, the development of new BCR-ABL1 mutations which potentially cause resistance to current treatment
 - At any time after the initiation of therapy, confirmed loss of MMR in 2 consecutive tests, of which one must have a BCR-ABL1 ratio $\geq 1\%$ IS
 - At any time after the initiation of therapy, new clonal chromosome abnormalities in Ph+ cells: CCA/Ph+
 - Intolerance is defined as:
 - Non-hematologic intolerance: Patients with grade 3 or 4 toxicity while on therapy, or with persistent grade 2 toxicity, unresponsive to optimal management, including dose adjustments (unless dose reduction is not considered in the best interest of the patient if response is already suboptimal)
 - Hematologic intolerance: Patients with grade 3 or 4 toxicity (absolute neutrophil count [ANC] or platelets) while on therapy that is recurrent after dose reduction to the lowest doses recommended by manufacturer
6. Eastern Cooperative Oncology Group (ECOG) performance status (PS) of 0, 1, or 2
7. Adequate end organ function as defined by (as per central laboratory tests):
 - Total bilirubin $\leq 1.5 \times$ ULN except for patients with Gilbert's syndrome who may only be included if total bilirubin $\leq 3.0 \times$ ULN or direct bilirubin $\leq 1.5 \times$ ULN

- Aspartate transaminase (AST) $\leq 3.0 \times \text{ULN}$
 - Alanine transaminase (ALT) $\leq 3.0 \times \text{ULN}$
 - Serum lipase $\leq 1.5 \times \text{ULN}$. For serum lipase $> \text{ULN} - \leq 1.5 \times \text{ULN}$, value must be considered not clinically significant and not associated with risk factors for acute pancreatitis
 - Alkaline phosphatase $\leq 2.5 \times \text{ULN}$
 - Creatinine clearance $\geq 50 \text{ mL/min}$ as calculated using Cockcroft-Gault formula
8. Patients must avoid consumption of grapefruit, Seville oranges or products containing the juice of each during the entire study and preferably 7 days before the first dose of study medications, due to potential CYP3A4 interaction with the study medications. Orange juice is allowed.
9. Written informed consent obtained prior to any screening procedures.
- 10a. Patients must have the following electrolyte values (as per central laboratory tests) within normal limits or corrected to be within normal limits with supplements prior to first dose of study medication:
- Potassium (potassium increase of up to 6.0 mmol/L is acceptable at study entry if associated with creatinine clearance within normal limits)
 - Total calcium (corrected for serum albumin); (calcium increase of up to 12.5 mg/dl or 3.1 mmol/L is acceptable at study entry if associated with creatinine clearance within normal limits)
 - Magnesium, with the exception of magnesium increase $> \text{ULN} - 3.0 \text{ mg/dL}$; $> \text{ULN} - 1.23 \text{ mmol/L}$ associated with creatinine clearance (calculated using Cockcroft-Gault formula) within normal limits.
11. Evidence of typical BCR-ABL1 transcript [e14a2 and/or e13a2] at the time of screening which are amenable to standardized RQ-PCR quantification.

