Purpose and rationale	
Purpose:
 
The purpose of this pivotal study is to compare the efficacy of asciminib with that of bosutinib in the treatment of patients with CML-CP having previously been treated with a minimum of two prior ATP-binding site TKIs with BCR-ABL1 ratios $\geq 1\%$ IS at screening. Patients intolerant to the most recent TKI therapy must have BCR-ABL1 ratio $> 0.1\%$ IS at screening and patients failing their most recent TKI therapy must meet the definition of treatment failure as per the 2013 ELN guidelines (Baccarani et al 2013). No more than 66 patients (approximately 30% of the overall trial population) that are intolerant to their most recent TKI therapy with BCR-ABL1 $< 1\%$ will be recruited in order to ensure that the CML third line patient population is adequately represented.
 
Rationale:
 
There remains an unmet need for new compounds in patients with CML who have failed at least two prior TKIs. Current practice suggests that a second generation TKI will have been used for first line therapy for about one half of patients with CML, meaning that most patients who have failed at least two prior TKIs will have failed at least one if not two second generation TKIs (such as dasatinib and/or nilotinib). Potentially, such patients may also have failed bosutinib and/or ponatinib (Soverini 2014). Patients having failed at least two TKIs may have limited sensitivity to the remaining available agents and, thus, there exists a need for new safe and effective therapy. In addition, mutations will have developed in 21 to 33% of patients that prevent the use of specific TKIs, increasing the need for a better and alternative compound (Soverini 2014). Omacetaxine, a chemotherapeutic agent, is available for patients who have failed at least two prior TKIs under these conditions but only in the US and Canada. This agent is not available for most patients globally, where a bigger unmet medical need is present. Thus, there remains an unmet need for patients with CML who have failed at least two prior TKIs despite the existence of multiple agents.

Primary Objective and Key Secondary Objective	
Primary Objective: To compare the Major Molecular Response (MMR) rate at 24 weeks of asciminib versus bosutinib
 
Key Secondary Objective: To compare MMR rate at 96 weeks of asciminib versus bosutinib

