Therefore, the threshold of $\geq 1\%$ BCR-ABL1 in the current trial is reduced to BCR-ABL1 ratio $> 0.1\%$ IS for patients with intolerance to most recent TKI treatment. No more than 66 patients (approximately 30% of the overall trial population) that are intolerant to their most recent TKI therapy with BCR-ABL1 $< 1\%$ will be recruited in order to ensure that the CML third line patient population is adequately represented. As the primary endpoint is the rate of MMR at 24 weeks a baseline molecular response level $> 0.1\%$ BCR-ABL1 is needed.

Patients experiencing documented treatment failure on bosutinib treatment will be allowed to switch to asciminib. Patients failing bosutinib treatment will have failed at least their third TKI treatment, with limited remaining treatment options. With this amendment patients who have failed bosutinib will be offered the possibility to continue in the study by receiving asciminib, if investigators consider that this treatment option is in the best interest of the patient. As of 15-Oct-2018, 4 patients could have potentially benefited from this option. Treatment failure during study treatment is assessed by measurable and pre-specified milestones defined by ELN criteria ([Baccarani et al 2013](#)), which are also used to define treatment failure as entry criteria for the study. Only documented treatment failure in the bosutinib arm will be considered for a treatment switch. For the purpose of the primary and secondary endpoint analyses, any patient meeting the ELN failure criteria while receiving study treatment, (either before or by the time of conducting the analysis and irrespective of treatment arm), will be considered as non-responders for the specific time point and for any subsequent time point. The switch to asciminib in case of bosutinib treatment failure is not expected to introduce bias as those patients will be regarded as non-responders irrespective of treatment switch and the disease burden will certainly not improve without further treatment. There is no option to switch patients failing on the asciminib treatment arm, as those patients can be offered approved

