10.1.6 Other analysis set

For duration of MMR and time to MMR, the MMR Responder Set that will be used is a subset of FAS and includes patients who achieve MMR at any time.

For CCyR rates at and by scheduled time points, the CCyR Analysis Set that will be used is a subset of FAS and includes patients who are not in CCyR at baseline.

For duration of CCyR and time to CCyR, the Cytogenetic Responder Set that will be used is a subset of FAS and includes patients who do not have CCyR at baseline and achieve CCyR at any time on study treatment.

Patients who will receive at least one dose of asciminib after bosutinib failure will form the Switch Analysis Set which will be used for safety and exploratory efficacy endpoints defined on these patients.

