10.4.1 Variable

The primary efficacy variable of the study is the Major Molecular Response (MMR) rate at 24 weeks. A patient will be counted as having achieved MMR at 24 weeks if he meets the MMR criteria (BCR-ABL1 ratio $\leq 0.1\%$) at 24 weeks.

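### The screening floor of BCR-ABL1 > 0.1% IS covers only intolerant patients, so a patient entered as a treatment failure can start the trial in MMR and count as a Week 24 responder

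*Combined protocol and SAP*

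**What the plan says.** **Entry.** Criterion 3a in section 5.2 sets the central-laboratory floor of BCR-ABL1 > 0.1% IS "according to central laboratory at the screening examination, for patients intolerant to the most recent TKI therapy". The protocol summary and sections 2.1 and 4.1 restrict it in the same way. A failure patient must meet at least one line of criterion 5. Two lines name no transcript level. One is the mutation line: "At any time after the initiation of therapy, the development of new BCR-ABL1 mutations which potentially cause resistance to current treatment". The other is the CCA/Ph+ line, which likewise can be met at any point on the last TKI.

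The loss-of-MMR line does name a level: "At any time after the initiation of therapy, confirmed loss of MMR in 2 consecutive tests, of which one must have a BCR-ABL1 ratio" of at least 1% IS. It does not require that value to come from the central screening sample. No exclusion criterion in section 5.3 covers MMR at entry.

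**Endpoint.** Section 10.4.1: "A patient will be counted as having achieved MMR at 24 weeks if he meets the MMR criteria", that is, a ratio of 0.1% or less at Week 24. Section 10.4.3 looks at status at that visit. The log reduction in section 7.2.1.1 is measured from the standardised baseline, not from the patient's own value. The primary analysis uses every randomised patient.

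**Contrast with CCyR.** Section 10.1.6 defines a CCyR Analysis Set that "includes patients who are not in CCyR at baseline", and its Cytogenetic Responder Set also leaves out patients in CCyR at baseline. The MMR Responder Set (called the Molecular Responder Set in section 10.5.2) has no such condition.

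**Purpose sentence.** The protocol summary still describes patients "having previously been treated with a minimum of two prior ATP-binding site TKIs with BCR-ABL1 ratios" of at least 1% IS at screening, and then gives the > 0.1% rule for intolerant patients.

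**The concern.** A patient who is in MMR at randomisation and still in MMR at Week 24 has kept a response, not achieved one. The sponsor recognises the principle. The Amendment 3 rationale says "As the primary endpoint is the rate of MMR at 24 weeks a baseline molecular response level" above 0.1% is needed, and explains that the floor was limited to intolerant patients because failing patients must meet the ELN-based criteria. For the two lines without a transcript level, meeting those criteria does not guarantee a value above 0.1%. I cite the rationale for intent only, not as a conflict between the amendment log and the current text.

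Three things are at stake: what the Week 24 and Week 96 MMR rates mean, some power, and the time-to-MMR summary. In that summary a patient in MMR at baseline would contribute roughly the date of the first on-study PCR.

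**Working it through.** **1. Which failure routes are compatible with MMR at screening**

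| Criterion 5 route | Transcript level named | Compatible with ≤ 0.1% at screening? |
|---|---|---|
| BCR-ABL1 > 10% IS at 6 or 12 months | yes | hard to reconcile |
| No CHR, or high Ph+ percentage | no | hard to reconcile |
| Loss of CHR, CCyR or PCyR | no | hard to reconcile |
| Confirmed loss of MMR | one test ≥ 1% IS | only if MMR was regained; doubtful, because criterion 5 opens by tying failure to the time of screening |
| New mutation | none | yes, on the text |
| New CCA/Ph+ | none | yes, on the text; the marrow may be up to 56 days old |

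**2. The plan's own figure.** Inputs from section 10.8: 15% v 35%, two-sided 5%, 90% power, 2:1 allocation. With pooled variance under the null and no continuity correction, let p̄ = (0.15 + 2 × 0.35)/3 = 0.2833. The bosutinib arm then needs

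n = [1.960 × √(1.5 × 0.2833 × 0.7167) + 1.282 × √(0.15 × 0.85 + 0.35 × 0.65/2)]² / 0.20² = 73.2, rounded up to 74.

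That gives 74 + 148 = 222, as stated. Power at 74/148 is 90.3% and the odds ratio is 3.05. The sample size is not in error.

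**3. Effect of patients already in MMR.** Let f be the share in MMR at entry. The documents do not give it. Assume it is equal in both arms, that all these patients are in MMR at Week 24, and that the planning rates hold for everyone else. Each rate becomes p(1 − f) + f, so the difference becomes 20 × (1 − f) points.

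| f (assumed) | Patients of 222 | Bosutinib | Asciminib | Difference (points) | Power | Share of bosutinib responders already in MMR at entry |
|---|---|---|---|---|---|---|
| 0 | 0 | 15.0% | 35.0% | 20.0 | 90.3% | 0% |
| 1% | 2.2 | 15.9% | 35.7% | 19.8 | 89.1% | 6% |
| 2% | 4.4 | 16.7% | 36.3% | 19.6 | 87.8% | 12% |
| 5% | 11.1 | 19.3% | 38.3% | 19.0 | 83.8% | 26% |

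If 95% rather than all of them keep MMR, power is 87.9% at f = 2% and 84.0% at f = 5%, so the result is not sensitive to that assumption.

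**4. One patient.** Replacing an average patient with one already in MMR shifts the arm's rate by (m − p)/n, where m is the chance of still being in MMR at Week 24.

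- Bosutinib: (1 − 0.15)/74 = 1.15 points, or (0.95 − 0.15)/74 = 1.08 points. About 1.1.
- Asciminib: (1 − 0.35)/148 = 0.44 points, or (0.95 − 0.35)/148 = 0.41 points. About 0.4.

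**The case against.** The best case for the plan has five parts.

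- **Failure must hold at screening.** Criterion 5 opens that way. A reader might infer that anyone who once lost MMR and then regained it on the same TKI qualifies. The documents do not clearly support this, and I treat that route as the less plausible one. The opening words set no transcript level, so they do not close the mutation and CCA/Ph+ routes.
- **The floor is a reasoned choice, consistently stated.** Sections 2.1, 4.1 and 5.2 agree with each other. A reader might infer that the protocol gives failure patients three competing floors (≥ 1%, > 0.1% and none). That overstates it: the > 0.1% figure for them comes only from amendment rationale, and the ≥ 1% figure from one summary clause. The operative rule is single, and it has a gap.
- **Stratification helps.** Patients in MMR would be expected mainly in the major cytogenetic response stratum, which randomisation balances and the CMH test adjusts for. This limits chance imbalance but does not remove it within a stratum, and it does not change who counts as a responder. The covariates of the logistic model are not fully listed, and baseline BCR-ABL1 level is not among the factors named in section 10.6.1.1.
- **ELN failures count as non-responders.** The Amendment 3 rationale says so, but it concerns failure on study treatment, not status at entry.
- **A rule may sit elsewhere.** The text reviewed is one part of a longer file, and section 10.6.2 defers some detail to an SAP. If a baseline-MMR rule exists there, citing it would settle the analytic part. None appears in sections 10.1 to 10.6 as reviewed; the deviations listed for the Per-Protocol Set do not include it.

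**Conclusion.** The concern holds as a statement of what the text permits. A failure patient, realistically through the new-mutation or CCA/Ph+ line, can be randomised in MMR and be credited with response at Week 24, and likewise at Week 96, which is derived in a similar way.

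The size depends on an unknown count that may be zero. At assumed shares of 1% to 2% the cost is one to three points of power; at 5% it is between six and seven points.

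A reader might infer that the gap favours asciminib. The documents do not support that. With randomisation and equal retention of MMR in the two arms, the expected effect is higher rates in both and a smaller difference. Chance imbalance matters most in the 74-patient bosutinib arm. Severity is minor to moderate.

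**What to change.** Amendment 03-US.01 records that recruitment finished on 22-Oct-2019, with 233 patients randomised. Rewording criterion 3a or adding an IRT check would not change who entered. The useful changes are analytic:

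1. Report, by arm, the number of randomised patients with a central screening BCR-ABL1 of 0.1% IS or less.
2. Add a sensitivity analysis of the Week 24 and Week 96 CMH tests that excludes them, labelled post hoc for any data already analysed.
3. Exclude them from the MMR Responder Set used for time to and duration of MMR, following the plan's own handling of CCyR.
4. Reconcile the summary's Purpose sentence with sections 2.1, 4.1 and 5.2.

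The data should be in hand: sections 7.1.2 and 7.1.2.4 require the RQ-PCR result before randomisation. The cost is one count, one extra table and slightly smaller sets in those analyses. If the count is zero, one sentence in the report closes the question for items 1 to 3.
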